Therefore, in the consent process we ask permission for conducting an annual survey and allowing the research team to follow their future health care and outcomes using a variety of data sources, including inspection of their VA and non-VA medical records, data from the Centers for Medicare and Medicaid Services (CMS), and VA and US death records (see Data Collection section below). We inform them that they will receive a small payment of a \$10 gift card for completion of the questionnaire and that the questionnaire has been pilot tested to make sure that it usually takes no longer than 30 minutes to complete. Subjects are also informed that they can choose to complete the questionnaire by phone if they prefer. Each subject is asked to assign a surrogate authorized to report vital status or health events (and provide a release of information) if the study subject is unable to do so. Of course, subjects are also informed that participation in the VADT-FS is completely voluntary and that they can revoke their consent at any point in the future.

We cannot be certain what will happen to the risk factor management of the VADT cohort once they return to routine VA primary care. If the previous experience of the DCCT-EDIC (Nathan, 2005) and the UKPDS Cohort hold true, then eventually both arms may converge toward a median A1c of about 7.8 – 8.0%. We suspect that the two study arms will have excellent and similar CV risk factor management during the observational follow-up period. Blood pressure and LDL levels are currently comparable in the two study arms, and based upon current VA-wide levels, we expect that blood pressure and LDL will remain generally well controlled during follow-up, at least compared to national averages. (Kerr, 2004; Asch, 2004; Kupersmith, 2007; Saydah, 2004)

VADT-FS Retention and Completion of Follow-Up

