Consented VADT-FS study subjects will be followed until the end of the study unless they withdraw their consent. The VADT-FS will also utilize several techniques to maximize a high level of study subject retention. For example, subjects who do not respond to the 3 mailed survey contacts will be contacted by phone and if that is not successful we will then try to contact their designated surrogate. If a subject does not complete the survey in a given year, the following year we will once again attempt to contact them as outlined above, unless they have withdrawn their consent. In addition to obtaining contact information on the study subject and their surrogate at the time of recruitment, we will obtain contact information for someone not living with the study subject who the study subject feels is likely to know how to contact the study subject over the next 10 years.

Data Collection Sources:

In order to ensure the integrity of the data a new unique ID number has been assigned to all patients involved in the VADT-FS. The unique ID consists of a five-digit number randomly assigned and has no reference to the original study ID or study site. The Hines CSPCC retains the cross-link between the Long Term Follow-up ID and the CSP #465 Study ID.

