(6) *Severe Visual Impairment*: defined as poor or worse visual function on the general visual function question on the National Eye Institute Visual Function Questionnaire.(Mangione, 2001; Naeim, 2006; Raphael, 2006)

(7) *Other major procedures/diagnoses*: categorized as, a) photocoagulation or vitrectomy, b) amputation.

(8) *Self-reported health status*: diabetes-related quality of life, using an instrument adapted for type 2 DM patients from the DCCT ([name], 1998; Saudek 1996). This survey tool has been used since the inception of the VADT and will be continued in the annual survey.

* $GFR (mL/min/1.73 m^2) = 175 \times (Cr)^{-1.154} \times (Age)^{-0.203} \times (0.742 \text{ if female}) \times (1.212 \text{ if African American})$

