Although eye disease is not a component of the VADT-FS's primary outcome, it is a very important component of a secondary outcome (major microvascular events). As above, the discontinuation of standard routine physical examinations makes continuation of visual acuity and retinopathy stage determinations problematic. Fortunately, there is now available a patient self-report visual function tool that has been developed with NIH support. (Mangione, 2001; Naeim, 2006; Raphael, 2006) This National Eye Institute Visual Function Questionnaire includes a validated single question for general visual function, and those reporting poor or worse function on this item have been validated to have substantial functional impairment impacting their quality of life (Mangione, 2001 and personal communication with [name] in January 2007). Although caution is always advised when including a new measure during the course of a longitudinal study, we feel that the adoption of this validated item measuring marked visual impairment is preferable to dropping measures of visual function altogether. Patients with reported visual problems will be informed that they can complete their surveys either using the assistance of their designated surrogate or by telephone, whichever they prefer.

Primary study end-point:

Major CV events (non-fatal MI resulting in hospitalization, non-fatal stroke, new CHF, amputation for ischemic diabetic gangrene, or CV-related death).

The proposed primary end-point of the VADT-FS is slightly more restrictive than the primary end-point of the VADT [excluding some CV procedures and subclinical AMI's based upon ECG changes alone] because the increased statistical power of the VADT-FS will allow greater focus on major clinical outcomes and avoid outcomes that are more difficult to discern (e.g., worsening of symptoms) or are more discretionary (e.g., cardiac

procedures).

Major secondary end-points:

1. CV mortality
2. Major microvascular complications (end-stage renal disease, or amputation for non-traumatic, non-ischemic diabetic gangrene).
3. Health-related quality of life (as measured by the modified DCCT tool on a 0-100 point scale)
4. Total mortality

Update

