Objective #2. To determine the long term effects of intensive glycemic control in type 2 diabetes on four secondary outcomes: a) cardiovascular mortality, b) major microvascular complications, c) health-related quality of life, d) total mortality, and e) major microvascular or macrovascular (end-stage renal disease, amputation for either ischemic or non-ischemic gangrene, CV-related death, or nonfatal MI, stroke, or new CHF). Statistical analyses for secondary outcomes will be identical to those used for the primary outcome, with the exception of microvascular complications and health related quality of life. Since one of the microvascular complications, severe visual impairment, is from the annual survey, survival analysis is not appropriate for the inaccuracy of the time of the record but logistic regression analysis. Since health related quality of life is a continuous measure, survival analysis will not be appropriate for this secondary outcome. The Student t-test will be used to evaluate for differences in mean quality-of-life scores in the two treatment arms, with use of robust methods if there is evidence that variance estimates vary between the two groups. It is well known that if there is a substantial difference in survival between intervention groups, health related quality of life results can be misleading unless the survival differences are accounted for. Therefore, if there are substantial differences in survival between treatment groups, an alternative analysis accounting for missing data due to mortality is a Bayesian imputation approach. (Revicki, 2001) Again, since substantive differences in baseline attributes did not occur, we do not feel that controlling for potential confounders using ordinary least squares regression is necessary.

Update

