In addition to examining interaction effects (factors that modify the intervention's effect), we will examine factors that are hypothesized to mediate the interaction effect. Whereas interaction effects are part of the experimental analysis (examining baseline [pre-randomization] subject attributes that identify individuals or groups who will benefit more or less than average), examination of potential mediating factors are observational analyses (examining factors post-treatment but prior to the occurrence of an outcome trying to better understand the treatment's mechanism(s) of action).(Hayward, 2006) There are two principle hypothesized mechanisms of action for why improved metabolic control may reduce CV events: 1) direct effects of hyper-glycemia on blood vessels and atherosclerotic disease, and 2) decreasing the prevalence of diabetic nephropathy and proteinuria (microvascular complications known to increase with hyperglycemia), which in turn reduces risk of CV events. We will examine these two factors following the methods used in the DCCT/EDIC.(Nathan, 2005) The variable examining direct hyperglycemic effects will be based upon the log of cumulative average A1c (previous observational analyses have consistently reported a log-linear association between A1c and adverse outcomes), which will be updated annually for all subjects who have not yet reached the endpoint. Markers for diabetic nephropathy previously reported to be associated with CV risk, include presence of proteinuria and estimated GFR. In addition to the log of cumulative average A1c, proteinuria and GFR, this analysis will control for a subject's other CV risk factors. (Fleiss, 1986) Cox proportional hazards regression will be used for these analyses, except for the visual impairment outcome which was not collected during the original VADT. Since time of the event is not available, logistic regression will be used for this outcome.

Missing Data

In longitudinal studies relying on survey or tests ordered in routine clinical practice, problems of missing data will almost always increase. Fortunately, our primary outcome and three of our four secondary outcomes do not rely on these data sources. However, our

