analysis of health related quality of life will be limited to those subjects who have answered the survey. For those analyses of interaction effects and potential mechanisms of action, outlined above, standard multiple imputation techniques will be utilized so as to prevent diminished sample size and potential response bias due to dropping subjects with missing data on covariates. (King, 2001; Revicki, 2001; Carroll, 1995) Imputed values for a given covariate will be informed by an individual's values for all other observed covariates to be used in the regression model, as well as temporal trends in the study population and previous values for that covariate in the individual. Multiple imputation is preferable in such instances, since it accounts for the degree of precision in imputed values and therefore provides better variance estimates for all regression coefficients. (King, 2001; Clayton, 1991; Carroll, 1995; Gatsonis, 1995; Oppenheimer, 1999)

Updates

There are no anticipated changes in the planned analyses, other than the addition of the new composite secondary endpoint, "Major Microvascular & Macrovascular Events" (see Endpoints Section) except severe visual impairment, which will be analyzed independently from other outcomes using only data collected through self-administered survey questionnaire during this follow-up period since 2009.

Study Significance.

The proposed extension of the VADT Follow-up Study (VADT-FS) would capitalize on a unique opportunity to examine factors that are associated with long-term complications and mortality for people with one of the most important conditions in modern medicine, a disease that will continue to grow dramatically if current epidemiological trends continue. Given the results of the UKPDS Follow-up Study and the DCCT-EDIC study, the objectives of the VADT-FS are important to answer in order to better assess possible multiplicative temporal effects and to obtain adequate statistical power to assess mortality benefits directly. It will also provide an opportunity to assess the long-term impact of tight glycemic control on vision and renal insufficiency when tight blood pressure control is achieved, a question unanswered by previous studies.

References:

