Annual Survey

Survey Instructions

- Please answer all questions as best you can
- All of your answers will be kept confidential
- Please return the completed questionnaire in the self-addressed, postage-paid envelope provided

Thank you so much for your time and assistance!

Would you prefer that we contact you by phone?

If because of visual problems or any reason whatsoever, you would prefer to complete this survey by phone, please contact us at [name] and ask for *[name]*.

Starts Approval Expires
12/16/13 IRB 10/06/14
Edward Hines, Jr. VAH/JALFHCC

CSP #465-F
VADT Long Term Follow-up Study

Form (70)
Annual Survey

I. General Health Questions:

1. In general, would you say your health is: **(Circle one)**

23 1 Excellent 2 Very Good 3 Good 4 Fair 5 Poor

2. The following questions are about activities you might do during a typical day. Does your health now limit you in these activities? If so, how much? **(Circle one)**

	Yes, limited a lot	Yes, limited a little	No, not limited at all
a. Moderate activities such as moving a table, pushing a vacuum cleaner, bowling, playing golf: _ _ _ _	24  1	 2	 3
b. Climbing several flights of stairs: _ _ _ _	25  1	 2	 3

3. During the past 4 weeks, how much of the time have you had any of the following problems with your work or other regular daily activities as a result of your physical health? **(Circle one)**

	All of the time	Most of the time	Some of the time	A little of the time	None of the time
a. Accomplished less than you would like? _ _ _ _ _	26  0	 1	 2	 3	 4
b. Were limited in the kind of work or other activities? _ _ _ _ _	27  0	 1	 2	 3	 4

4. During the past 4 weeks, how much of the time have you had any of the following problems with your work or other regular daily activities as a result of any emotional problems? **(Circle one)**

	All of the time	Most of the time	Some of the time	A little of the time	None of the time

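### Read literally, the severe-visual-impairment analysis leaves out telephone-completed surveys, a route the plan offers specifically to people with visual problems

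*Combined protocol and SAP*

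**What the plan says.** The outcome is a single survey item, "defined as poor or worse visual function on the general visual function question" (Measuring Endpoints, endpoint 6; item 8 of the annual survey). The Updates under Missing Data take it out of the joint analyses and say it will be analysed on its own, "using only data collected through self-administered survey questionnaire during this follow-up period since 2009".

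Other parts of the plan create completion routes besides the mailed form:

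- Measuring Endpoints: "Patients with reported visual problems will be informed that they can complete their surveys either using the assistance of their designated surrogate or by telephone", with the choice left to the patient.
- Survey cover (Appendix D): "If because of visual problems or any reason whatsoever, you would prefer to complete this survey by phone", followed by a contact for doing so.
- VADT-FS Recruitment: "Subjects are also informed that they can choose to complete the questionnaire by phone if they prefer".
- VADT-FS Retention and Completion of Follow-Up: "subjects who do not respond to the 3 mailed survey contacts will be contacted by phone", and then the designated surrogate is tried. The Self Report section also describes telephone attempts at 3 months.

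Two other statements bear on the source of the outcome. Objective #2 in the Analysis Plan says that "severe visual impairment, is from the annual survey", with no limit on mode. Evaluation of Mechanisms of Action refers to the "visual impairment outcome which was not collected during the original VADT" and specifies logistic regression for it.

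**The concern.** The plan opens a telephone route with poor sight expressly in mind, then restricts the poor-sight outcome to self-administered forms. Nothing in the documents says that telephone answers count as self-administered. An analyst who follows the Missing Data wording would remove valid answers, and would remove them more often from people who cannot comfortably read the form. Another analyst, following Objective #2, would keep them. One plan could therefore yield two datasets. Because the outcome is a single survey item with no other source, a discarded answer cannot be recovered elsewhere. At stake are the reported prevalence of severe visual impairment, the number of events in the comparison and, under a further condition set out in the working, the estimate itself.

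**Working it through.** The plan states no event rate, power or mode split for this outcome, so there is no figure to reproduce. The check is textual first, then illustrative.

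**Text.** The Missing Data restriction has two parts: a period (follow-up, since 2009) and a mode (self-administered). The period alone already excludes original-trial eye data. The mode therefore reads as an additional filter, and it conflicts with the telephone routes listed above. Surrogate help is less clear, since a mailed form filled in with help can still be called self-administered.

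**Inputs from the documents.** Main Cohort 1,031 (Statistical power, Update); 2011 survey response 82.7% (Self Report, Updates); effect size 0.8, borrowed from Table 2, where it is a hazard ratio, and used here as a risk ratio.

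**Assumed inputs.** Equal arms; true standard-arm prevalence p = 10% (range 5% to 15%); 5% of unimpaired respondents excluded; a fraction f of impaired respondents excluded, 10% to 60%.

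**Respondents.** 1,031 × 0.827 = 853, or about 426.5 per arm in one survey round.

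**Observed prevalence** = p(1 − f) / [p(1 − f) + (1 − p) × 0.95].

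- f = 30%: 0.070 / (0.070 + 0.855) = 7.6%.
- f = 50%: 0.050 / (0.050 + 0.855) = 5.5%.

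**Events and power** (two-proportion normal approximation, two-sided 0.05, true risks 10% and 8%). Events with nothing excluded: 426.5 × (0.10 + 0.08) = 76.8. Events kept = 76.8 × (1 − f).

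| f | Events kept | Observed standard-arm prevalence | Power |
|---|---|---|---|
| none excluded | 77 | 10.0% | 0.17 |
| 10% | 69 | 9.5% | 0.16 |
| 30% | 54 | 7.6% | 0.14 |
| 50% | 38 | 5.5% | 0.11 |
| 60% | 31 | 4.5% | 0.10 |

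At f = 60%, power falls from 0.11 to 0.07 if true prevalence is 5%, and from 0.25 to 0.13 if it is 15%.

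**Odds ratio, same f in both arms.** Exclusion multiplies the odds of impairment in each arm by (1 − f)/0.95. The factor cancels, so the odds ratio stays at (0.08/0.92) / (0.10/0.90) = 0.78.

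**Odds ratio, f differing by arm.** If 20% of impaired intensive-arm and 40% of impaired standard-arm respondents were excluded, the odds ratio would be 0.783 × (0.80/0.60) = 1.04.

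**Odds ratio, f depending on severity.** Suppose the standard arm has 5% poor and 5% very poor or blind, treatment halves only the latter, and 20% and 60% of these groups are excluded.

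- True odds ratio: (0.075/0.925) / (0.100/0.900) = 0.73.
- Cases kept, intensive arm: 0.05 × 0.8 + 0.025 × 0.4 = 0.050. Standard arm: 0.05 × 0.8 + 0.05 × 0.4 = 0.060.
- Observed odds ratio: (0.050/0.925) / (0.060/0.900) = 0.81. The common 0.95 cancels.

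**The case against.** The best answer is that no exclusion was meant. No section says that telephone or surrogate-assisted answers will be discarded. Objective #2 names the annual survey without qualification, the recruitment section treats the telephone as another way to complete the same questionnaire, and the item was not collected in the original trial. The restriction may therefore mean only that follow-up survey data are used, rather than original-trial eye data. Discarding telephone answers would also defeat the accommodation made in Measuring Endpoints. This reading is plausible. It does not settle the matter, because the period limit already conveys it and the word for the mode remains.

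A reader might also infer that the plan steers visually impaired people away from the mailed form, or that the comparison between arms is necessarily biased towards no difference. The documents support neither. The telephone and surrogate routes are offered by preference, and the telephone is open to everyone. Exclusion that depends on impairment alone leaves the logistic odds ratio unchanged, and the documents give no evidence that mode use differs by arm.

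Two further limits stand. The illustration treats one survey round. Over repeated surveys, someone who once reported poor sight by mail would still be counted if the outcome is ever being impaired, so the loss could be smaller. And power is low even with every answer kept, so the wording changes little about what the comparison can show.

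**Conclusion.** The wording conflict is real and minor. Applied as written, the rule drops telephone-completed surveys, understates prevalence and loses events. With 10% true prevalence, and 30% to 50% of impaired and 5% of unimpaired respondents excluded, observed prevalence would be about 7.6% to 5.5%. At a risk ratio of 0.8, power would fall from 0.17 to between 0.14 and 0.11. The exclusion fractions and the prevalence are assumptions, so the true size is unknown. Bias in the odds ratio needs the further condition that mode use among impaired subjects differs by arm, for example because treatment alters severity. The primary outcome is not affected, since vision is not part of it.

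**What to change.** In the Updates under Missing Data, replace *self-administered survey questionnaire* with *the annual survey, however completed (mail, telephone, or with surrogate help)*. This agrees with Objective #2. If completion mode is on file, show the mail-only result as a sensitivity analysis.

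The cost is one phrase and no new data. The small downside is that answers given by different modes are pooled, which the sensitivity analysis would let a reader judge.

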Appendix B
VADT Endpoint Definitions

CSP #465 (VADT) Endpoint Definitions

PRIMARY ENDPOINTS

1. MYOCARDIAL INFARCTION

Myocardial infarctions will be determined based on the algorithm supplied at the end of this appendix. All suspected MI will be evaluated in detail by the Endpoints Committee. All supporting documentation, i.e., ECGs, hospital records, laboratory values, etc. needed to confirm or rule out the presence or absence of an MI will be obtained by personnel at the ECG Laboratory.

2. CONGESTIVE HEART FAILURE – also see revised definition below:

Diagnosis of new congestive heart failure (CHF) can be made in the presence of at least two major manifestations of CHF or one major and at least two minor manifestations or new onset of pulmonary congestion requiring treatment. Treatment with diuretic, digitalis glycoside, ACE inhibitor, or hospitalization for management of symptoms of CHF would be appropriate.

Major Criteria:

- 1) paroxysmal nocturnal dyspnea
- 2) distended neck veins
- 3) cardiomegaly and pulmonary hilar congestion on X-ray, or increased heart size
- 4) acute pulmonary edema
- 5) increased venous pressure
- 6) hepatojugular reflux
- 7) documented 10% or greater decrease in ejection fraction to less than 40%.

Minor Criteria:

- 1) bilateral ankle edema
- 2) night cough
- 3) dyspnea on normal exertion
- 4) hepatomegaly
- 5) pleural effusion

Diagnosis of worsening CHF, for patients entering the Study with NYHA Class I or II CHF, will be made if there is a 10% (absolute) decrease in LVEF. Baseline assessment of LVEF must be made within the six months prior to randomization.

REVISED CHF DEFINITION: meets all criteria shown above with the additional requirement that the patient will have been hospitalized or had an urgent care visit associated with aggressive treatment for CHF as part of the event. Aggressive treatment today (2003) primarily includes intravenous treatment with diuretics and/or inotropic agents. However, as the study progresses, this list may be expanded to include newer oral agents. The aim of this additional condition is to ensure that the visit was accompanied by, if not precipitated by, moderate to severe CHF symptoms.”

